2.2 Secondary Objectives

None

3 Study details

3.1 Study design

This is a Post Marketing Observational Study (PMOS), an open, non-interventional study. The patients will be treated in accordance with normal routine care and the drug will be prescribed in accordance with the approved labeling (Summary of Product Characteristics), i.e. AbbVie will not be involved in the supply of Adalimumab.

Patients will be included in the study at the time the physician has decided to change their current treatment to Adalimumab for any reason. The decision to prescribe Adalimumab should be clearly separated from and preceding the decision to include the patient in the study. The patients will be assessed during routine visits at the clinic at baseline (inclusion) and after approximately 4 weeks, 12 weeks and 24 weeks. Data will be collected from the patient's medical records, by investigator assessment and by patient questionnaires as described in section 9.1.1 Study Flow Chart and in Section 9.3 Variables.

3.1.1 Study Flow Chart

Patients that have been prescribed Adalimumab as per routine care will asked to participate in this study. In accordance with routine care, a patient will be seen by the patient's physician at baseline (inclusion) and approximately 4, 12 and 24 weeks after the first dose of Adalimumab.

Parameters	Baseline	Week 4	Week 12	Week 24
Informed consent	Х			
Demographic/baseline data	Х			
Dermatology Life Quality Index (DLQI)	Х	Х	Х	Х

EuroQol (EQ-5D)	Х	Х	Х	Х
Patient's Global Assessment of Skin Pain (NRS)	X	Х	Х	Х
Work Productivity and Activity Impairment	Х	Х	Х	Х
Questionnaire: Specific Health Problem				
(WPAI:SHP)				
Hidradenitis Suppurativa Impact Assessment	Х	Х	Х	Х
(HSIA)				
Hidradenitis Suppurativa Clinical Response	Х	Х	Х	Х
(HiSCR)				
Serious Adverse Event		Х	Х	Х
Pregnancy Reporting		Х	Х	Х
Concomitant Medication	Х	Х	Х	Х
Surgical Treatment	Х	Х	Х	Х
Missed Adalimumab doses		Х	Х	Х

3.2 Number of patients

3.2.1 Sample size calculations

With 50 evaluable patients, the power is 90% based on a change in DLQI of -5.4, and an assumed standard deviation of 11.5 and type I error of 5% (two-sided). The dropout rate is considered to be low, approximately 5% after 12 weeks, which will have a minimal impact on the power (decreased to 88%).

3.2.2 Interim analysis

An interim analysis will be performed in Q2 of 2017 for administrative reasons. No statistical analyses will be presented and no adjustments regarding this interim analysis are planned for the final analysis.

3.3 Randomization

NA This is a Post Marketing Observational Study

3.4 Database lock

When the database has been declared to be complete and accurate, the database will be locked and declared clean file. Any changes to the database after that time can only be made by joint written agreement between the project manager, the data manager and the statistician.

4 Analysis Sets

4.1 Definition of analysis data sets

The analysis of data will be based on different subsets according to the purpose of analysis, i.e. for effectiveness and safety respectively. The decision regarding validity of data for each of the analysis sets will be made before database lock.

4.2 Baseline analysis set

The Baseline analysis set will include all enrolled patients, with the exception of subjects who had no baseline data collected.

The Baseline analysis set will be used for presenting baseline characteristics.

4.3 Effectiveness analysis sets

4.3.1 Full analysis Set (FAS), (modified Intention-to-treat(ITT)

The FAS will include all enrolled patients, with the exception of subjects who were enrolled and not treated with any dose of adalimumab, or who had no baseline or post baseline data collected for the primary endpoint Dermatology Life Quality Index (DLQI). In case all of a patients post baseline assessments of DLQI are outside visit windows, the patient is excluded from FAS.

The FAS will be used for baseline characteristics and analysis of effectiveness.

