9.3.5 Clinical Effectiveness

HiSCR is a clinical endpoint focusing on assessment of HS inflammatory signs and symptoms that will determine the clinical effectiveness of Adalimumab.

Assessment will be performed by the physician at baseline and at 4, 12 and 24 weeks. HiSCR requires:

- At least a 50% reduction in the total abscess and inflammatory nodule count (AN count) relative to baseline, and
- No increase in abscess count, and
- No increase in draining fistula count.

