5.3 Safety endpoints

• Non-serious Adverse events

As the safety profile of Adalimumab is stable and well established, non-serious events will not be actively solicited as these events are not likely to further contribute

to the understanding of the safety profile of the product. Any non-serious reports will be collected as spontaneous reports if notified to AbbVie.

• Serious Adverse events

Serious adverse events will be reported to AbbVie from the time the physician obtains the patient's authorization to use and disclose information (or the patient's informed consent) until 30 days or 5 half-lives following the intake of the last dose of physician-prescribed treatment.

In the CRF the response to the following question is registered at 4, 12 and 24 week visits:

Has any SAE(s) occurred since last visit?

6 Analysis Methods

The final statistical analyses will be performed at Scandinavian Development Services AB, Danderyd, Sweden by using the SAS ® version 9.3 or higher.

Continuous variables will be summarized using descriptive statistics (n, mean, SD, min, median, max). Categorical variables will be summarized in frequency tables (frequency and proportion). Graphical presentations, e.g. describing the change over time, will be used as appropriate, and individual patient data will be listed.

The primary and secondary endpoints (change in DLQI, Patient's Global Assessment of Skin Pain (NRS), EQ-5D VAS score and WPAI:SHP at 4, 12 and 24 weeks) will be analyzed using paired samples t-tests or non-parametric methods such as Wilcoxon signed rank test as appropriate.

HiSCR is a dichotomous response variable which will be analysed descriptively presenting proportion HiSCR with binomial exact 95% confidence interval.

The change at 12 weeks will be of primary interest.

Visit windows regarding 4, 12 and 24 weeks assessments following first dose of Adalimumab will decide the validity of assessment.

•	Baseline	Last assessment before first dose of Adalimumab
•	4 weeks	Day $(4*7)$ - $(3*7) \ll 4$ weeks \ll Day $(4*7)$ + $(3*7)$

•	12 weeks	Day (12*7)-(4*7)	<= 12 weeks <= Day (12*7)+(4*7)
•	24 weeks	Day (24*7)-(7*7)	<= 24 weeks <= Day (24*7)+(7*7)

Assessments outside these visit windows will not be part of input for summaries by visit. Such assessments will only be presented in listings.

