6.2.1 Missing data

In general imputation of missing observations will not be performed. Missing data will be reported descriptively.

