6.4 Effectiveness analyses

Effectiveness analyses will be based on the Full analysis Set (FAS), as described in earlier sections, using paired samples t-tests or non-parametric methods such as Wilcoxon signed rank test as appropriate for numerical endpoints. Dichotomous response variables which will be analysed descriptively presenting proportion of responders with binomial exact 95% confidence interval.

The PP analysis set will be used as sensitivity analysis for the primary effectiveness endpoint.

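### FAS entry depends on usable DLQI data, yet the FAS is used for every effectiveness endpoint, so any treated patient lacking only the DLQI drops out of the other summaries too

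*SAP*

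**What the plan says.** SAP 4.3.1 starts from all enrolled patients and removes those who received no adalimumab and those "who had no baseline or post baseline data collected for the primary endpoint Dermatology Life Quality Index (DLQI". It adds a window condition: "In case all of a patients post baseline assessments of DLQI are outside visit windows, the patient is excluded from FAS".

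The set so defined serves all effectiveness work. SAP 4.3.1 states: "The FAS will be used for baseline characteristics and analysis of effectiveness". SAP 6.4 repeats it, "Effectiveness analyses will be based on the Full analysis Set (FAS), as described in earlier sections", and covers numerical and dichotomous endpoints alike.

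The effectiveness endpoints other than DLQI (Protocol 8.0, SAP 5.2) are skin pain NRS, EQ-5D (items and VAS), HSIA items, WPAI scores and HiSCR. The first four come from separate questionnaires. HiSCR comes from lesion counts made by the clinician; Protocol 9.3.5 says: "Assessment will be performed by the physician at baseline and at 4, 12 and 24 weeks". Its analysis is given in SAP section 6: "HiSCR is a dichotomous response variable which will be analysed descriptively presenting proportion HiSCR with binomial exact 95% confidence interval".

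On missing values, SAP 6.2.1 says: "In general imputation of missing observations will not be performed".

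**The concern.** None of the other five instruments needs a DLQI score to be computed, yet a patient's place in their summaries depends on one. A treated patient with a blank baseline DLQI but complete lesion counts at all four visits would be missing from the HiSCR proportion at weeks 4, 12 and 24, and likewise from the pain, EQ-5D, HSIA and WPAI results.

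This follows from a stated rule; it is not a gap in the text. Protocol 7.3 says that national data on quality of life, pain, work productivity and activity may be needed to support reimbursement. With about 50 patients, it is worth avoiding exclusions from those results that have nothing to do with the outcome reported.

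**Working it through.** **1. Does another analysis set restore these patients?**

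| Set (SAP) | Membership | Use |
|---|---|---|
| Baseline, 4.2 | Enrolled, with baseline data | Baseline characteristics |
| FAS, 4.3.1 | Treated, with usable DLQI | Baseline characteristics and all effectiveness |
| PP, 4.3.2 | Subset of FAS | Sensitivity analysis, primary endpoint only |
| Safety, 4.4 | Treated, with safety follow-up | Safety endpoints |

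No. The PP set lies inside the FAS and has one role: "The PP analysis set will be used as sensitivity analysis for the primary effectiveness endpoint". The other two sets serve other purposes. SAP section 7 does not mention the restriction, and the protocol defines no analysis sets. The interim listings are not affected, because SAP 6.1.5 bases them on all enrolled patients without windows.

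**2. How is the exclusion to be read?** The wording could mean that either baseline or post-baseline DLQI is missing, or that both are. The next sentence of 4.3.1 excludes on post-baseline grounds alone. Under the both-missing reading, a patient with no post-baseline DLQI would stay in, while one with only out-of-window DLQIs would go out. The either-missing reading is the natural one and is used here.

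**3. Who is lost only because of the DLQI?** The windows in SAP section 6 are:

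- Week 4: 28 ± 21, days 7 to 49
- Week 12: 84 ± 28, days 56 to 112
- Week 24: 168 ± 49, days 119 to 217

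Between day 7 and day 217 only days 50–55 and 113–118 are uncovered, 6 + 6 = 12 days. All instruments are scheduled at the same visits. If a DLQI is out of window, the other assessments made that day are too, and section 6 already keeps them out of the by-visit summaries. Early drop-outs will usually lack the other data as well. What remains is a patient whose DLQI is unusable at baseline, or at every attended in-window visit, while other assessments from those visits exist. The documents give no number for this group. Nor does the SAP say whether a partly completed DLQI counts as data collected.

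**4. The plan's own figure.** SAP 3.2.1 gives 90% power with 50 evaluable patients, falling to 88% after about 5% drop-out. For a two-sided paired t-test with change 5.4, SD 11.5 and alpha 0.05, the noncentrality is (5.4/11.5) × √50 = 3.32.

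- n = 50: power 90.2%
- n = 48: power 89.0%
- n = 47: power 88.3%

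The figures reproduce. They concern DLQI, to which a patient without a DLQI change cannot contribute, so this point leaves them as they are.

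**5. Possible effect on HiSCR (assumed numbers).** Let N = 50 treated patients have HiSCR data, x of them responders, and let k be excluded only for DLQI. The FAS proportion then lies between (x − k)/(N − k), if all k are responders, and x/(N − k), if none is.

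With x = 25 and k = 3, and exact 95% intervals:

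- All patients: 25/50 = 50.0% (35.5 to 64.5)
- All 3 excluded are responders: 22/47 = 46.8% (32.1 to 61.9)
- All 3 excluded are non-responders: 25/47 = 53.2% (38.1 to 67.9)

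If the 3 were excluded at random, the chance that all are non-responders is C(25,3)/C(50,3) = 2300/19600 = 11.7%, and the mirror case is equally likely.

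The week-12 adalimumab rates quoted in Protocol 7.2.2 are 41.8% and 58.9%. Taking 21/50 and 30/50 as nearby whole counts gives:

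| k | 21/50 = 42.0% | 30/50 = 60.0% |
|---|---|---|
| 2 | 39.6% to 43.8% | 58.3% to 62.5% |
| 3 | 38.3% to 44.7% | 57.4% to 63.8% |
| 5 | 35.6% to 46.7% | 55.6% to 66.7% |

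The extreme shift is about 2 to 7 percentage points for k from 2 to 5. If exclusion is unrelated to outcome, only precision suffers: for k = 3 the standard error rises by a factor of √(50/47) = 1.03.

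**The case against.** The best defence is that the rule is fixed in advance, openly labelled a modified intention-to-treat set, and gives one common population across endpoints. That is a legitimate choice. The affected group is narrow for the reasons in step 3 and may be empty. The excluded values are not hidden, since individual patient data will be listed. HiSCR is secondary and descriptive, and a shift of 3.2 points sits inside intervals nearly 30 points wide. All of this stands, and it limits the weight of the point. It does not supply a reason why a lesion count or a pain score should depend on a DLQI form.

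A reader might go further and infer that the response rate is selected upwards because patients doing poorly stop filling in questionnaires. The documents do not support that as a general claim. Baseline is the last assessment before the first dose (SAP section 6), so a blank baseline DLQI cannot result from poor response to treatment. The mechanism needs a patient who keeps attending for lesion counts but has no usable in-window DLQI at any post-baseline visit. That is possible, but nothing in the documents suggests it is common. Likewise, it would be wrong to say that the plan discards the data of five instruments at large: it drops them from the summaries, and only for this small group.

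**Conclusion.** The point holds in a limited form. The plan makes summaries of HiSCR, NRS, EQ-5D, HSIA and WPAI conditional on usable DLQI data, and no other set restores the patients affected. The certain cost, if any such patients exist, is some precision. Bias is possible in either direction; selection through poor response can enter only through missing post-baseline DLQI. The size depends on an unknown count: the shifts of about 2 to 7 points assume that 2 to 5 of 50 patients are affected and that all of them fall on the same side. The conclusion also rests on the either-missing reading of 4.3.1. This is a minor, optional improvement.

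**What to change.** Keep the FAS in SAP 4.3.1 as it is for the DLQI analyses. Add a sentence to 4.3.1 and 6.4 saying that each other effectiveness endpoint is analysed in all patients with at least one dose of adalimumab who have a baseline value and an in-window post-baseline value of that endpoint. For HiSCR, this means the lesion counts. Report n for each endpoint and visit.

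No new data are needed. The cost is that denominators differ slightly between endpoints, which already happens because missing values are generally not imputed.

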4.3.2 Per protocol analysis set (PP)

Criteria for the determination of the PP population will be finalized prior to database lock, and will include the following:

- Study subjects included in FAS
- Study subjects meeting all inclusion criteria and none of the exclusion criteria
- Study subjects with a valid 12 week assessment(according to visit windows) for the primary endpoint Dermatology Life Quality Index
- Study subjects who up until the valid 12 week assessment have less than 4 missed doses of Adalimumab

The PP analysis set will be used as sensitivity analysis for the primary effectiveness endpoint.

4.4 Safety analysis set

The safety analysis set will include all subjects given at least one dose of adalimumab and for whom follow-up safety data are available. Subjects/data will be summarised and analysed according to the total dose dispensed.

The Safety analysis set will be used for analysis of safety endpoints.

5 Endpoints

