9.3 Variables

9.3.1 Demographic/baseline data

The following data will be collected at the baseline visit:

- Demographic/Baseline data
 - Age, gender and ethnicity
 - Smoking habits
 - Body Mass Index (BMI)
 - Age when HS symptoms started
 - Date of diagnosis
 - HS assessment (lesion count and Hurley stage)

- Adalimumab treatment start (info on missed doses will be collected at 4, 12 and 24 weeks)
- Previous treatment(s) for HS
- Previous surgery for HS (info on new surgeries for HS will be collected at 4, 12 and 24 weeks)
- Co-morbidities
- Concomitant medications (changes in Concomitant Medication will be collected at 4, 12 and 24 weeks)

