6.2.3 Treatment group comparisons

NA This is a Post Marketing Observational Study analyzing only one treatment group

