6.5 Safety analyses

Responses to the CRF question "Has any SAE(s) occurred since last visit?" will be summarized descriptively for the 4, 12 and 24 week visits.

7 Changes of Analyses from Protocol

It was specified in Protocol that HiSCR was to be analyzed using t-test or non-parametric methods such as Wilcoxon signed rank-test.

HiSCR is a dichotomous response variable which will be analysed descriptively presenting proportion HiSCR with binomial exact 95% confidence interval.

It was specified in Protocol that HSIA and EQ5D was to be analyzed using t-test or non-parametric methods such as Wilcoxon signed rank-test.

No total scores for HSIA or EQ5D will derived. Both endpoints will be analyzed descriptively presenting result by sub-item. The EQ5D VAS score has however been added as one variable to be analysed using paired samples t-tests or non-parametric methods such as Wilcoxon signed rank test as appropriate

8 References

The numbered references present in section 1 Introduction are found in the Study protocol.

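### SAP 4.4 calls for safety analysis by total dose dispensed, which is not listed as collected and conflicts with SAP 6.2.3 and 6.5, and its follow-up condition is undefined

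*SAP*

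**What the plan says.** SAP 4.4 does two things. It sets membership: "The safety analysis set will include all subjects given at least one dose of adalimumab and for whom follow-up safety data are available". It then gives a rule for presentation: "Subjects/data will be summarised and analysed according to the total dose dispensed".

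Other parts of the plan bear on both:

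- SAP 3.1, like Protocol 9.1, places the drug in routine care: "AbbVie will not be involved in the supply of Adalimumab".
- Protocol 9.3.1 lists the dosing information to be recorded: "Adalimumab treatment start (info on missed doses will be collected at 4, 12 and 24 weeks"). The flow charts in Protocol 9.1.1 and SAP 3.1.1 add only a row for missed doses.
- SAP 6.2.3 describes the study as "analyzing only one treatment group".
- SAP 6.5, the only safety analysis specified, reads: "Responses to the CRF question 'Has any SAE(s) occurred since last visit?' will be summarized descriptively for the 4, 12 and 24 week visits".
- Protocol 11.1.4 and SAP 5.3 have SAEs reported from consent until a set time after the last dose. Protocol 11.1.5 has the site enter them in the EDC system within 24 hours of learning of them. Neither depends on a study visit.
- SAP 6.3.1 tabulates the number and percentage of patients in the safety set.

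**The concern.** The dose sentence names a grouping variable that the plan gives no means of obtaining, and it contradicts two other SAP sections. A programmer following SAP 4.4 would have to invent both the variable and the categories.

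The likely substitute is a total dose built from treatment start and missed doses. That quantity accrues after baseline. A patient who stops because of an SAE has a low total dose as a result of the SAE, so a table by dose could suggest that less drug goes with more SAEs when no such relation exists.

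The membership rule raises a separate question. Follow-up safety data is not defined, and the specified summary uses only answers given at the week 4, 12 and 24 visits. A treated patient with an SAE report in the EDC but no follow-up visit could fall out of the set, or stay in it and add nothing to the table. SAEs are the only adverse events actively sought in this study, so their denominator and source should be unambiguous.

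**Working it through.** The documents state no SAE rate, so there is no plan figure to reproduce on this point.

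**1. Can the dose rule be carried out?**

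| Needed for SAP 4.4 | What the documents provide |
|---|---|
| Amount dispensed per patient | Not listed in Protocol 9.1.1 or 9.3.1, or in SAP 3.1.1; no study supply |
| A usable substitute | Treatment start and missed doses, which at most approximate doses taken, not dispensed |
| Dose categories | None defined |
| A table to apply it to | SAP 6.5 has no dose split; SAP 6.2.3 has one group |
| A recorded change from the protocol | SAP section 7 does not mention a dose-based safety analysis |

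The rule cannot be carried out from the listed variables.

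**2. What would an approximated split do?**

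Let x_F of n_F patients with a full course and x_S of n_S with a shorter course have an SAE. Suppose SAE risk is unrelated to dose, and a share q of SAE patients stop because of the event.

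- If q = 0, the expected rates x_F/n_F and x_S/n_S are equal, and there is no artefact.
- If q > 0, some SAE patients move from the full-course row to the shorter-course row. The first rate falls and the second rises.
- The overall proportion is (x_F + x_S)/(n_F + n_S). Moving patients between rows leaves it unchanged: with 3 SAE patients among 50, it is 3/50 = 6.0% for every q.

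The documents do not give q, so the size of a false contrast cannot be stated.

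**3. What could the follow-up condition do?**

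Inputs: 50 patients (SAP 3.2.1, assumed here all treated) and expected dropout of about 5% after 12 weeks (same section), so 0.05 × 50 = 2.5, or 2 to 3 patients. Patients with no follow-up by then should be among these, so m = 1 to 3 is examined. Assumed: 3 patients with follow-up report an SAE at some visit.

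Reported proportion = 3/(50 − m). True proportion = 3/50 if none of the m had an SAE, or (3 + m)/50 if each had one that went uncounted.

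| m | Reported | True, none had an SAE | True, each had an SAE |
|---|---|---|---|
| 1 | 3/49 = 6.1% | 3/50 = 6.0% | 4/50 = 8.0% |
| 2 | 3/48 = 6.25% | 6.0% | 5/50 = 10.0% |
| 3 | 3/47 = 6.4% | 6.0% | 6/50 = 12.0% |

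Exact (Clopper-Pearson) 95% intervals: 3/50, 1.3 to 16.5%; 3/47, 1.3 to 17.5%; 6/50, 4.5 to 24.3%. Changing the denominator alone does almost nothing. Losing the events is what matters, and the last column is a worst case.

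**The case against.** The strongest reply is that SAP 6.5 governs. It specifies a summary of a yes/no question by visit with no dose split, and that table can be produced whatever SAP 4.4 says. This stands. A reader might infer from SAP 4.4 that the SAE table cannot be made, or that the dose rule would mis-state the overall SAE risk. The documents support neither: a split would distort only the comparison between dose rows, and only if some patients stop after an SAE.

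A reader might also infer that dispensed dose is not collected at all. The eCRF is not shown and Protocol 9.4 draws on medical records, so the safe statement is that it is not listed as collected.

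On the follow-up condition, SAEs are reported independently of visits, so a patient with an SAE report arguably has follow-up safety data and stays in the set. That is a fair reading, but the SAP does not say so. Under SAP 6.5 as written, such a patient without a visit answer would still not be counted. SAP 6.3.1 shows the size of the set and individual data are listed, so exclusions would be visible. That reduces the harm but does not settle the definition.

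Finally, putting every treated patient in the denominator treats those without follow-up as having had no SAE, which pulls the proportion down. That is a real, small cost of the change.

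**Conclusion.** The dose sentence in SAP 4.4 is a wrong rule, not merely a missing detail. It conflicts with SAP 6.2.3 and 6.5, rests on a variable not listed as collected, and has no categories. This follows from the text without assumptions. Any misleading dose-SAE pattern is conditional on an approximated split being made and on stopping after SAEs, for which the documents give no rate. The overall SAE proportion is unaffected.

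The follow-up condition is a smaller but real gap. Its effect runs from negligible (6.4% against 6.0%) to 6.4% reported against 12.0% true. The upper end assumes 50 treated patients, 3 counted SAE patients and 3 patients without follow-up who each had an uncounted SAE.

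Severity is minor: this is a descriptive safety summary in a single group of about 50 patients.

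**What to change.** Before database lock:

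1. Delete the dose-dispensed sentence from SAP 4.4.
2. Define the safety set as all patients given at least one dose, summarised as one group, with no follow-up condition.
3. In SAP 6.5, report the number and proportion of patients with at least one SAE, taken from the SAE reports in the EDC, alongside the visit question.
4. State how many treated patients had no follow-up, and give the proportion among those with follow-up as well. Define follow-up explicitly, for example as at least one visit answer to the SAE question.

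The cost is a few lines of SAP text and one table definition, using data the plan already lists. The small downside is that patients without follow-up count as non-events in the all-treated proportion, which is why both denominators are shown. SAEs never reported to the site or sponsor would remain uncounted under either denominator.
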